1. OVERVIEW

1.1 Study Objectives

1.1.1 Primary Objective

- To determine the optimal dose of VLA15 in healthy adults aged 18 - 65 years up to Day 85.

1.1.2 Secondary Objectives

Immunogenicity:

- To assess the immune response of VLA15 in healthy adults aged 18 - 65 years up to Month 12 (i.e. 10 months after the primary vaccination series).

Safety:

- To assess the safety profile of VLA15 in healthy adults aged 18 - 65 years up to Month 12.

1.2 Study Design

This is a randomized, observer-blind (subject, sponsor and investigator/ site staff involved in clinical evaluation of subjects are blinded), placebo controlled, multicenter Phase 2 study (see Figure 1).

In the Run-in phase, a total of 120 subjects aged 18 to 40 years were to be randomized stratified by study site 1:1:1:1 to receive VLA15 90 µg w/ alum, VLA15 135 µg w/ alum, VLA15 180 µg w/ alum, or placebo (30 subjects per treatment group) as intramuscular (I.M.) vaccinations on Days 1, 29 and 57. Dosing was to be adjusted by injection volume (see Table 1).

Table 1: Treatment Groups and Vaccinations

Group	Treatment	Injection Volume [mL]	Days of Vaccination
90 µg	VLA15 90 µg w/ alum	0.50	1, 29, 57
135 µg	VLA15 135 µg w/ alum	0.75	1, 29, 57
180 µg	VLA15 180 µg w/ alum	1.00	1, 29, 57
Placebo	PBS	1.00	1, 29, 57

Two safety visits were to be performed after the first vaccination: a safety phone call at Day 4 (i.e. Visit 1a, three days after the first vaccination) and an in-person visit at Day 8 (i.e. Visit 1b, seven days after the first vaccination). After all subjects enrolled in the Run-in phase completed Visit 4 (Day 85, i.e. 28 days after the third vaccination) a Data Safety Monitoring Board (DSMB) reviewed all available safety data up to Day 85 in a scheduled DSMB meeting and gave the recommendation that all treatment groups were safe and well tolerated so far and could be continued in the Main Study phase based on available safety data. After the DSMB meeting, the two higher dose groups (135 µg and 180 µg of VLA15 w/ alum) were selected for further investigation. No safety concerns associated with any of the VLA15 treatment groups were identified by the independent DSMB.

In the Main Study phase, a total of 450 subjects aged 18 to 65 years will be randomized stratified by study site, age group and baseline *B.b. s.l.* serostatus 2:2:1 to receive 135 µg or 180 µg VLA15 w/ alum (180 subjects each) or placebo (90 subjects), as I.M. vaccinations on Days 1, 29 and 57. Subjects will be enrolled in two age groups (18-49 years and 50-65 years) in a ratio of approximately 2:1.

In both study phases, target is to enroll approximately 10 % or more of subjects that are baseline seropositive for *Borrelia burgdorferi sensu latu* (*Bb s.l.*). This is aimed to be achieved through selection of endemic recruitment areas as well as database searches for *Bb s.l.* seropositive subjects.

1.3 Endpoints

1.3.1 Primary Endpoint

- Geometric Mean Titers (GMTs) for Immunoglobulin G (IgG) against each Outer surface protein A (OspA) serotype ST1 to ST6, determined by Enzyme-Linked Immunosorbent Assay (ELISA) at Day 85.

1.3.2 Secondary Endpoints

Immunogenicity:

- GMTs for IgG against each OspA serotype (ST1 to ST6), determined by ELISA, at Day 1, 29, 57, 180, 236, and Month 12;
- Seroconversion rates (SCRs) for each OspA serotype specific IgG (ST1 to ST6), determined by ELISA, at Day 29, 57, 85, 180, 236, and Month 12;
- Geometric Mean Fold Rise (GMFR) as compared to baseline for IgG against each OspA serotype (ST1 to ST6), determined by ELISA, at Day 29, 57, 85, 180, 236 and Month 12;
- GMTs, SCRs and GMFRs for IgG against each OspA serotype (ST1 to ST6), determined by ELISA, at Day 1, 29, 57, 85, 180, 236, and Month 12, stratified by age group.

Safety:

- Frequency of Serious Adverse Events (SAEs) during the entire study;
- Frequency of related SAEs during the entire study;
- Frequency of Adverse Events of Special Interests (AESIs) during the entire study;
- Frequency of related AESIs during the entire study;
- Frequency of unsolicited Adverse Events (AEs) during the entire study (incl. clinically relevant laboratory parameters);
- Frequency of related unsolicited AEs during the entire study (incl. clinically relevant laboratory parameters);
- Frequency of solicited local and solicited systemic AEs within 7 days after each and after any vaccination.
- Frequency of SAEs, AESIs, solicited and unsolicited AEs during the entire study stratified by age group.

1.4 Sample Size Calculation

The sample size for the Run-in phase has been chosen to allow detection of common AEs with the three initial dose levels. 30 Subjects will provide 95 % confidence that an AE not seen in the Run-in phase would have a true incidence of below 10 %.

The overall group size for the two doses (VLA15 w/ alum 135 µg and VLA15 w/ alum 180 µg) evaluated in the Main Study phase has been selected to provide a sufficient safety database and for determining the optimal dose before advancing the vaccine candidate into Phase 3. Upon completion of the study, the total number of subjects exposed to the dose used for Phase 3 trials would be a minimum of approximately N=210. The database would thus allow 95 % confidence that a given reaction would not be observed at a higher rate than 1:(210/3) rate, i.e. 1.4 %, if it is not observed in the trials preceding Phase 3.

[figure not shown]
With respect to the primary endpoint, GMTs for ST1-6 specific IgGs on Day 85: In the absence of an established protective titer, sample size calculation is based on somewhat arbitrary differences in GMTs between VLA15 treatment groups, in order to demonstrate which titer levels could be distinguished with the proposed sample size. Titers observed in Phase 1 were used as basis: In the 90 µg w/ alum group (i.e. the lowest dose group used in the present Phase 2 study), a GMT of 61.3 was observed for ST1 (i.e. the serotype with lowest titers in Phase 1) with a Standard Deviation (LOG10) of 0.51. A total of 189 subjects per group (assuming 10 % of the 210 subjects per treatment group are excluded from primary Per-protocol (PP) analysis) will provide 80 % power at a two-sided alpha level of 5 % to distinguish a GMT of 61.3 in one treatment group from a putative higher GMT of 86.1 in another dose group. An approximately 1.5 fold higher titer could thus be distinguished. A 1.5 fold difference in GMTs is often considered a relevant difference in vaccine studies, e.g. when setting non-inferiority boundaries.

The overall sample size of 120 subjects in the placebo group has been selected to allow for the internal validation of both safety and immunogenicity results.

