2.14 Changes in the Conduct of the Study or Planned Analysis

Statistical analysis will be conducted as described in this SAP. Any deviations or changes will be described and justified in the CSR.

- It was stated in the protocol that an interim analysis on safety and immunogenicity data will be performed after all subjects have completed Visit 6 (i.e. Day 236, six months after the last vaccination) and that this interim analysis will cover safety and immunogenicity data up to Visit 4 as well as safety data up to Visit 6. This interim analysis will be conducted in 2 parts, a IA Day 85 covering all safety data up to Day 85 and immunogenicity data from Day 1 and Day 85. The second part will cover all safety data up to Day 236 (see Section 2.1). The first part of the Interim Analysis only starts after the last subject completed Visit 6 or the time window for Visit 6 has elapsed.

- The following adjustments concerning statistical analysis as compared to descriptions in the protocol are included in this SAP: The protocol planned to only compare the two dose groups selected for the main phase and the placebo group. However, it was decided to include all dose groups in the comparison. In particular, the pair-wise comparison between the two dose groups selected for the main phase and the placebo group, respectively, will be part of the comparisons that will be performed.
- It was stated in the protocol that all time points up to Day 85 will be included in interim immunogenicity analysis. However, only Day 1 and Day 85 will be analyzed in the IA Day 85. All time points will be analyzed in the Final Analysis.
- Due to optimization of the ELISA assay, the definition for seroconversion for ELISA results was adjusted as compared to the protocol, see Section 5.2.
- Functionality of antibodies will be measured by a Serum Bactericidal Assay (SBA). Analysis of SBA parameters will be described in a separate SAP and is not part of the interim analysis described here.

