5.2 Derivations and Definitions

- Baseline for immunogenicity analysis is defined as Visit 1.
- A subject reaches a 4-fold increase if the value at a certain visit after Day 1 is at least 4-times higher than the value at Day 1. 10-fold increase will be derived analogously.
- Baseline OspA IgG seropositive/seronegative for ELISA is defined as follows:
 - ELISA samples scored as “negative” or below the quantitation limit of the ELISA (40 U/mL) will be replaced by 20 U/mL.
 - Subjects with Day 1 (Visit 1) values below the quantitation limit of the ELISA (40 U/mL) and samples scored as “negative” (i.e. replaced by 20 U/mL) will be considered “baseline OspA IgG seronegative” for each serotype.

- Subjects with Day 1 (Visit 1) values of 40 U/mL and above are considered “baseline OspA IgG seropositive” for each serotype.
- Seroconversion is defined as:
 - For subjects that are seronegative at Visit 1 (baseline): a change from seronegative at Visit 1 to seropositive (i.e. antibody titer of ≥ 40) at a certain time point.
 - For subjects that are seropositive Visit 1 (baseline): a ≥ 4 -fold rise in IgG antibody titer from Visit 1.
 - In case of missing values (missing at baseline or current time point), seroconversion is not calculated.

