5.3 Inferential analysis

- In general, all statistical tests comparing treatment groups in the immunogenicity analysis will only include the two dose groups chosen for the main phase (i.e. VLA15 135 μ g and 180 μ g groups) and the placebo group. However, summary measures for 90 μ g group will be included in the tables.
- ANOVAs with factors treatment group and study sites will be performed for the comparison between the VLA15 135 μ g, 180 μ g and Placebo group for each OspA ST1 to ST6 respectively. The primary immunogenicity analysis will be the ANOVA for ELISA GMTs at Day 85 in the PP Population.
- ANOVAs will be performed for GMTs as well as GMFRs at all available time points.
- This will be done using log10 transformed data and taking the anti-log of the resulting point estimates for the least squares means, least squares means differences and the corresponding 95% CIs. Tukey's HSD test will be applied for pair-wise comparisons.
- Sensitivity analyses for GMTs and GMFRs will be performed for ANOVAs with factors study site, treatment group, study site*treatment group, age, and B.b. s.I serostatus at baseline.
- Summary tables for the OspA- specific IgG titer against each OspA serotype and summary tables for the geometric mean fold-rise against each OspA serotype will be amended by an overall test (Kruskal-Wallis).
- SCRs will be compared using Fisher-Freeman-Halton tests, a significant overall test will be amended by pair-wise tests (Fisher's exact test). The same will be done for rates of subjects reaching a 4- or 10- fold Increase from Day 1 (Visit 1) in titer.
- A non-parametric correlation analysis (Spearman) between OspA IgG antibodies GMTs for each combination of two different OspA specific IgG types will be performed for Day 85 and VLA15 treatment group separately as well as for all VLA15 treatment groups together (pooled analysis).

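### The 80% power in SAP Section 1.4 is for one unadjusted test of a 1.40-fold difference; under the planned three-group Tukey HSD it is about 68%, and 80% is reached at about 1.47-fold

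*SAP*

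**What the plan says.** Section 1.4 takes two Phase 1 values for ST1 at 90 µg with alum: a GMT of 61.3 and a log10 SD of 0.51. It removes 10% of 210 subjects per dose group to reach 189 and states that this number "will provide 80 % power at a two-sided alpha level of 5 % to distinguish a GMT of 61.3" in one group from 86.1 in another. It mentions no multiplicity adjustment. The next sentence draws the conclusion: "An approximately 1.5 fold higher titer could thus be distinguished".

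Section 5.3 fixes the analysis: "The primary immunogenicity analysis will be the ANOVA for ELISA GMTs at Day 85 in the PP Population". The model has factors treatment group and study site, the groups are 135 µg, 180 µg and placebo, and Tukey's "HSD test will be applied for pair-wise comparisons".

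Section 2.14 describes the groups differently. It reports that the protocol compared only the two selected doses and placebo, and continues: "However, it was decided to include all dose groups in the comparison".

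**The concern.** The comparison of 135 µg with 180 µg is one of the pairs that Section 5.3 sends through Tukey's HSD. That procedure uses a larger critical value than an unadjusted 5% test, so a power figure that ignores it describes a different test. Section 1.4 also does not agree with itself: 86.1 is 1.40 times 61.3, yet the conclusion drawn from that pair is about 1.5-fold.

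The primary objective is to find the optimal dose, and Section 1.4 is the only place where the plan says how well the primary analysis can separate two doses. If the 135 vs 180 µg contrast is not significant, a reader would credit the trial with a 20% risk of missing a 1.40-fold difference. Under the planned test with a common SD, that risk is about 32%.

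**Working it through.** **Inputs from the SAP.** Section 1.4: GMTs 61.3 and 86.1, log10 SD 0.51, 189 evaluable per dose group, placebo 120. Section 5.3: three groups, Tukey's HSD.

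**Assumption.** Placebo loses the same 10%, leaving 108. This enters through the error degrees of freedom (189 + 189 + 108 − 3 = 483) and, if the placebo SD differs, through the pooled SD.

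**1. The plan's own figure**

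- Fold: 86.1 / 61.3 = 1.4046; log10 difference 0.1475.
- Standard error of the difference: 0.51 × √(2/189) = 0.0525.
- Noncentrality: 0.1475 / 0.0525 = 2.81.
- Unadjusted two-sided 5% t-test, df 376, critical |t| 1.966: power **80.1%**; 80% power at 1.404-fold.

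The stated 80% is therefore one unadjusted comparison.

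**2. The planned test (three-group Tukey, common SD 0.51, no gain from site)**

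- Critical |t| = q(0.95; 3, 483) / √2 = 3.3248 / √2 = 2.351, a per-pair two-sided alpha of about 1.9%.
- Power for 61.3 vs 86.1, normal approximation: Φ(2.81 − 2.351) ≈ 0.68. Noncentral t: **67.8%**. Simulation agrees (67.8%, 400,000 runs).
- 80% power is reached at **1.471-fold**; 61.3 × 1.471 = 90.2.
- At 1.5-fold: log10(1.5) / 0.0525 = 3.36, power **84.2%**.
- Other placebo sizes (up to 189) and site counts (1 to 20) change only the degrees of freedom. Power stays at 67.8% within rounding.

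**3. Placebo SD**

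The plan gives no placebo SD. It could be small, because ELISA results "below the quantitation limit of the ELISA (40 U/mL) will be replaced by 20 U/mL" (Section 5.2). The ANOVA pools the error, so the pooled SD is √[(376 × 0.51² + 107 × SD²) / 483], and the effective critical value is 2.351 × pooled SD / 0.51.

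| Placebo log10 SD | Pooled SD | Nominal power at 1.40-fold | Fold at 80% power | Site share of variance needed for 80% at 1.40-fold |
|---|---|---|---|---|
| 0.51 | 0.510 | 67.8% | 1.471 | 22.5% |
| 0.25 | 0.465 | 74.8% | 1.434 | 11.3% |
| near 0 | 0.450 | 77.0% | 1.422 | 7.0% |

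The lower two rows are nominal. The gain arises because the pooled error understates the variability of the two vaccine groups being compared. Even a placebo group with no variance does not bring power to 80% without help from site.

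**4. If Section 2.14 governs (four groups)**

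Assume 27 evaluable at 90 µg (30 less 10%) and a common SD. The critical |t| is 2.578. Power is 59.3% at 1.40-fold and 78.2% at 1.5-fold, and 80% needs 1.51-fold.

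**The case against.** Five points can be made for the plan.

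- **The arithmetic is right for what it describes.** Section 1.4 speaks of one group against another at two-sided 5%, and 80% follows. That stands. The fault is the mismatch with the test in Section 5.3.
- **The working conclusion holds.** About 1.5-fold is detectable with 84% power under three-group Tukey, and rounding 1.40 up is cautious. This stands too, and is why no design change is needed. But the 1.5 is presented as following from 61.3 vs 86.1, which it does not.
- **The 68% is the low end.** A small placebo SD plus a site effect of 7% to 11% of variance would restore nominal 80%. That is fair, and 68% should not be quoted without its assumptions. The plan states neither assumption, so it cannot rely on them for its 80%.
- **The inputs are soft.** The SD comes from Phase 1, and Section 2.14 reports that the ELISA has since been optimised. Under three-group Tukey, an SD of 0.45 gives about 80% power at 1.40-fold and 0.55 about 60%. This limits any claim about the trial's true power. It does not make an unadjusted figure right for a Tukey test.
- **Little turns on it now.** Section 1.4 calls the differences somewhat arbitrary, no decision rule in the SAP uses the 80%, Day 85 visits are complete (Section 2.15), and confidence intervals will be reported. This limits the consequence to how a null dose comparison is read.

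**Conclusion.** The concern holds. The stated 80% belongs to an unadjusted comparison of 61.3 with 86.1. The planned three-group Tukey HSD gives about 68% for that pair and reaches 80% at about 1.47-fold, assuming 189/189/108 evaluable subjects, a common log10 SD of 0.51 and no variance explained by site. With a smaller placebo SD, nominal power is 75–77%. It reaches 80% only if site also explains a share of variance that the plan does not mention. About 1.5-fold remains a fair summary under three-group Tukey, but not quite at 80% power under a four-group family, so the conflict between Sections 2.14 and 5.3 bears directly on the figure. All these powers are per serotype, with no adjustment across ST1 to ST6.

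**What to change.** Restate the power sentence in Section 1.4 with its test and assumptions, for example:

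> With 189 PP subjects per dose group and a log10 SD of 0.51, one unadjusted two-sided 5% comparison has 80% power for GMTs of 61.3 and 86.1 (1.40-fold). Under the planned Tukey HSD over 135 µg, 180 µg and placebo, assuming a common SD and no variance reduction from study site, power for this difference is about 68%. Power of 80% is reached at about 1.47-fold (61.3 vs about 90), i.e. roughly 1.5-fold. Power is per serotype.

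A further clause could say that a smaller placebo SD or a site effect would raise nominal power, so that 68% is not read as unconditional.

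Reconcile Sections 2.14 and 5.3 first, so that the number of groups in the Tukey family is fixed. If the family has four groups, use the corresponding figures (about 59% at 1.40-fold, 78% at 1.5-fold, 80% at 1.51-fold, with 27 evaluable at 90 µg assumed).

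The cost is a few sentences in Section 1.4 and one reconciled statement on the groups compared. If Section 5.3's three groups are confirmed, sample size, primary test and estimates are unchanged.

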1.5 Flowchart

1.5.1 Study Design

Figure 1: Study Design

1.5.2 Study Schedule

Table 2: Table of Events – Run-in-Phase

Visit	V0	V1	V2	V3	V4	V5	V6	V7	Early Termination (1)
Timing Day (D)	D-21	D1	D29 M1	D57 M2	D85 M3	D180 M6	D236 M8	D365 M12	before V7
Time windows	-21 to -1	0	+/- 4	+/- 4	+/- 4	+ 7/- 14	+ 7/- 14	+/- 14	n/a
Visit type	In-person	In-person	In-person	In-person	In-person	In-person	In-person	In-person	In-person
Informed consent (2)	X	X	X (Review)						
Inclusion/exclusion criteria	X	X	X	X					
Vaccination delay criteria	X								
Demographic data	X								
Medical history incl. vaccinations	X	X (3)							
Concomitant medication/s/ treatments incl. vaccinations	X	X	X	X	X	X	X	X	X
Physical examination (4), ECG	X								
Vital signs (5)	X	X	X	X	X	X	X		
Evaluation of oral body temperature	X	X (6)	X (6)	X (6)	X (6)				
HIV test [3.5 mL] (7)	X (26)								
Bb s1 screening test [4mL] (8)	X (26)								
Baseline serology sample [5.0 mL] (9)	X (26)								
Serum pregnancy test [3.5 mL] (10)	X (26)								
Urine Pregnancy test (10)		X (11)	X (11)	X (11)	X (11)	X (11)	X (11)	X (11)	X (11)
Clinical chemistry [8.5 mL] (12)	X (26)		X (11)	X (11)	X (11)	X (11)	X (11)	X (11)	X (11)
Hematology [4 mL] (13)	X (26)		X (11)	X (11)	X (11)	X (11)	X (11)	X (11)	X (11)
Coagulation blood sample [4.5 mL] (14)	X (26)								
Urinalysis (15)		X (11)	X (11)	X (11)	X (11)	X (11)	X (11)	X (11)	X (11)
Immunogenicity blood sample. (16)		X (11)	X (11)	X (11)	X (11)	X (11)	X (11)	X (11)	X (11)
	[54 mL]	[27 mL]	[54 mL]	[54 mL]	[54 mL]	[54 mL]	[27 mL]	[27 mL]	[54 mL]
Randomization (17)		X	X	X	X	X	X	X	X
VACCINATION (18)		X	X	X	X	X	X	X	X
Check for AEs following vaccination		X	X	X	X	X	X	X	X
Symptom-driven physical exam (19)		X (20)	X (20)	X (20)	X (20)	X (20)	X (20)	X (20)	X (20)
Inspection of injection site of previous vaccinations			X (21)	X (21)	X (21)	X (21)	X (21)	X (21)	X (21)
Distribute and explain Subject Diary (22)		X	X	X	X	X	X	X	X
Review and collect Subject Diary		X	X	X	X	X	X	X	X
Distribute and explain Memory Aid									X (23)
Review and collect Memory Aid									X (23)
AE/ SAE/ AESI Assessment (24)		X	X	X	X	X	X	X	X
Blood volume [mL]	33.0 (10); 29.5 (25)	54.0	39.5	66.5	66.5	27.0	27.0	70.5	4.0

Adapted from:
 STAT03_A Statistical Analysis Plan
 Version 6.0, Effective Date 16-Feb-2018
 Confidential and intellectual property of [REDACTED]
 No part of this document or its contents may be duplicated, referenced, published or otherwise disclosed in any form or by any means without prior written consent of [REDACTED]

Table 3: Table of Events – Main Study Phase

Visit	V0	V1	V2	V3	V4	V5	V6	V7	Early Termination (1)
Timing Day (D)	D-21	D1	D29	D57	D85	D180	D236	D365	before V7
Month (M)	-21 to -1	0	M1	M2	M3	M6	M8	M12	n/a
Time windows	In-person	In-person	+/- 4	+/- 4	+/- 4	+7/-14	+7/-14	+/- 14	
Visit type			In-person						
Informed consent (2)	X								
Inclusion/exclusion criteria	X	X (Review)							
Vaccination delay criteria		X	X						
Demographic data	X								
Medical history incl. vaccinations	X	X (3)							
Concomitant medications/ treatments incl. vaccinations	X	X	X	X	X	X	X	X	X
Physical examination (4), ECG	X								
Vital signs (5)	X	X	X	X	X	X	X	X	
Evaluation of oral body temperature	X	X (6)	X (6)	X (6)					
HIV test [3.5 mL] (7)		X (26)							
Bb s.i. screening test [4 mL] (8)		X (26)							X
Baseline serology Sample [5.0 mL] (9)		X (26)							X
Serum Pregnancy test [3.5 mL] (10)		X (26)	X (11)	X					
Urine Pregnancy test (10)			X (11)	X					
Clinical chemistry [8.5 mL] (12)		X (26)	X (11)	X					
Hematology [4 mL] (13)		X (26)	X (11)	X					
Coagulation blood sample [4.5 mL] (14)		X (26)	X (11)	X					
Urinalysis (15)		X	X (11)	X					
Immunogenicity blood sample, (16)		X (11)	[54 mL]	[54 mL]	[54 mL]	[54 mL]	[27 mL]	[27 mL]	[54 mL]
Randomization (17)		X	[27 mL]						
VACCINATION (18)		X	X						
Check for AEs following vaccination		X	X						
Symptom-driven physical exam (19)		X (20)	X (20)	X (20)	X (20)	X (20)	X (20)	X (20)	
Inspection of injection site of previous vaccinations			X (21)	X					
Distribute and explain Subject Diary (22)	X	X	X	X	X	X	X	X	
Review and collect Subject Diary		X	X	X	X	X	X	X	X (23)
Distribute and explain Memory Aid									
Review and collect Memory Aid									X (23)
AE/ SAE/ AESI Assessment (24)	X	X	X	X	X	X	X	X	X
Blood Volume [mL]	33.0 (10); 29.5 (25)	54.0	39.5	66.5	66.5	27.0	27.0	70.5	4.0

(1) Every effort should be made to have discontinued subjects complete the early termination visit. If the subject is unwilling to perform an ET visit, a phone-call should be made to follow-up on Adverse Events and Concomitant Medications/ Vaccinations. Note: If a subject presents at a regular study visit and informs that it will discontinue the study after this visit, the study visit will not be performed as an ET visit, but as a regular study visit including all events that are described for the respective study visit; but in addition, a Lyme borreliosis screening test will be performed.

(2) Occurs before screening and prior to any study-related procedures.

Adapted from:

STAT03_A Statistical Analysis Plan
Version 6.0, Effective Date 16-Feb-2018
Confidential and intellectual property of [REDACTED]

No part of this document or its contents may be duplicated, referenced, published or otherwise disclosed in any form or by any means without prior written consent of [REDACTED]

(3) Symptoms noted at Visit 1 (prior to first vaccination) are not considered AEs but will be recorded as medical history.

(4) Physical examination on following body systems: general appearance, skin, head/abdomen, extremities and joints, lymph nodes, and neurological system. If applicable, physical examination as well as ECG performed within the study VLA15-202 is acceptable for study VLA15-201 if within the specified visit window.

(5) Vital signs (Systolic and diastolic blood pressure and pulse rate while seated and at rest) to be measured prior to vaccination and in addition prior to discharge in case subject reports any complaints.

(6) To be performed prior to vaccination.

(7) The results of negative HIV tests that were performed up to 30 days before Visit 0 are acceptable (blood: HIV test 3.5 mL). Positive HIV test obtained by ELISA will have to be confirmed by a second method (e.g. Westernblot or PCR).

(8) A commercially available C6 ELISA assay (ViSE ELISA) will be performed (blood: 4 mL). Serum samples that are tested positive will have to be verified by a confirmatory immunoblot. Test results need to be available before randomization and remain valid for 4 weeks.

(9) A baseline serology sample will be taken in the screening visit and might be used for work-up of suspected LB-associated, autoimmune or neuroinflammatory events (e.g. analysis of Rheumatoid factor (RF), anti-citrullinated protein antibodies (ACPA), etc. as appropriate), (blood: 5.0 mL). If applicable, a baseline serology sample collected at the study site within the study VLA15-202 is acceptable for study VLA15-201 if within the specified visit window.

(10) In women of childbearing potential, A woman is considered of childbearing potential if fertile, following menarche and until becoming post-menopausal unless permanently sterile. A woman that is considered of non-childbearing potential must be e.g. surgically sterilized for at least 3 months prior to Visit 1 (e.g. by hysterectomy, bilateral salpingectomy, bilateral oophorectomy, transcervical sterilization), or postmenopausal for at least one year prior to Visit 1. For serum pregnancy test: tests that were performed in study laboratory within visit window and where results are available at study visit are acceptable.

(11) At vaccination visits, all samples have to be obtained before vaccination. Pregnancy results and urinalysis must be available before vaccination.

(12) Creatinine, sodium, potassium, calcium, aspartate aminotransferase (AST), alanine aminotransferase (ALT), alkaline phosphatase, bilirubin, CRP (blood: 8.5 mL). Test results of current visit do not need to be available before vaccination. Tests that were performed in study laboratory within visit window and where results are available at study visit are acceptable.

(13) Hemoglobin, hematocrit, erythrocyte count, white blood count, platelets (Ethylenediaminetetraacetic acid [EDTA] blood: 4 mL). Test results of current visit do not need to be available before vaccination. Tests that were performed in study laboratory within visit window and where results are available at study visit are acceptable.

(14) Prothrombin time, aPTT, fibrinogen (blood: 4.5 mL). Tests that were performed in study laboratory within visit window and where results are available at study visit are acceptable.

(15) Standard urine dipstick: pH, specific gravity, leucocytes, nitrite, protein, glucose, ketones, urobilinogen, bilirubin, erythrocytes. Tests that were performed in study laboratory within visit window and where results are available at study visit are acceptable.

(16) Blood will be collected for immunogenicity testing by ELISA and for supportive functional antibody analysis by e.g. growth inhibition assay, surface binding assay or serum transfer experiments (passive protection animal model). *

(17) To be performed by study staff otherwise not involved with study conduct to keep the study observer-blinded (i.e. unblinded study staff)

(18) Study vaccine has to be administered by study staff otherwise not involved with study conduct to keep the study observer-blinded. Subjects enrolled in the Run-in phase should be observed for at least one hour, subjects enrolled in the Main Study phase should be observed for at least 30 min after vaccination for treatment of any immediate reactions.

(19) Except for Visit 1: Body systems for which the subject reports any symptoms should be evaluated and relevant abnormal findings documented as AEs. At vaccination days the symptom-driven physical exam is to be performed before administration of the vaccination.

(20) If subject has any complaints after vaccination, a second symptom-driven physical examination will be performed by the investigator prior to discharge.

(21) The injection site of previous injections should be evaluated by study staff prior to the next vaccination.

(22) At Visit 1, the subjects will be provided with thermometer and measuring tapes. The subjects will assess solicited local and systemic AEs themselves over a period of seven consecutive days after each vaccination.

(23) Unreturned Subject Diaries/ Memory Aids should be collected at the Early Termination Visit. For Early Terminations prior to Visit 4, the previous injection site should be inspected.

(24) AEs, SAEs and AESIs will be collected throughout study conduct. Symptoms noted at Visit 1 (prior to vaccination) are not considered adverse events but will be recorded as medical history.

(25) Women of non-childbearing potential and male subjects.

(26) If applicable, HIV test, Lyme borreliosis screening test, serum pregnancy test, clinical chemistry tests, hematology tests, and coagulation tests performed at the study site within the study VLA15-202 are acceptable for study VLA15-201 if within the specified visit window. As such, if test results are available, respective blood samples do not need to be collected again for the present study. Similar, if applicable, a baseline serology sample collected at the study site within the study VLA15-201 if within the specified visit window.

* Functional antibody analysis will be provided using a serum bactericidal assay.

Adapted from:
 STAT03_A Statistical Analysis Plan
 Version 6.0, Effective Date 16-Feb-2018
 Confidential and intellectual property of [REDACTED]
